6.1.1.7 HOME CSII TREATMENT PHASE

During the home CSII treatment phase participants will use the investigational/control CSII catheter in combination with the Medtronic MiniMed insulin pump for diabetes management. Participants will follow their regular lifestyle, adjusting basal infusion rate, meal bolus doses and correction doses according to their routine clinical methods. They will use their diabetes diaries to document VAS pain score, signs/symptoms of hypoglycemia, treatment of hypoglycemia, CSII catheter issues, and overall health. BG will be measured continuously by the CGM device.

Study participants will receive detailed instructions regarding diabetes care plan, including dietary guidelines, treatment of hyperglycemia, hypoglycemia, and the management of CSII catheter failure. Participants will be instructed to monitor their blood ketone levels if their CGM or SMBG values are greater than 250 mg/dL for more than 2 hours or they develop signs/symptoms of diabetic ketoacidosis.

Table 7: Participant instruction for at home use

Patient Diary (daily)	Participant records: 
 ▪ Hypo-/hyperglycemic episodes ▪ Insertion site assessments ▪ Insertion set failure ▪ Other device issues or complications ▪ VAS Pain Scale (daily insertion site comfort levels)
Insertion Site Assessment (daily)	Participant visually inspects and records insertion site findings (i.e. skin reaction or infection)
Dexcom G6® CGM	Records glucose values throughout study

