Secondary Endpoints 4:	
 • Proportion of investigational CSII sets that did not fail on each day of use. • Mean difference across treatments in time to device failure • Mean difference across treatment in incidence of pump bolus occlusion alarms • Mean difference across treatment in incidence of pump basal occlusion alarms

Safety Objectives:	To assess Achilles infusion set safety and tolerability from DOI through day 7 for each treatment
Safety Endpoints:	
 • The occurrence hyperglycemia (glucose >250 mg/dL) not responsive to a pump bolus dose where response to the bolus is defined as a fall of at least 50 mg/dL in blood glucose within one hour, • The occurrence of hyperglycemia (glucose >250 mg/dL) after prolonged fasting (e.g. overnight or more than 5 hours following a meal), not associated with acute intercurrent illness, but with a concurrent ketone level ≥ 0.6 mmol/L. • Localized infection or inflammation of greater than 1.0 cm in diameter at the infusion site • Occurrence of an insulin pump occlusion alarm signal • Cannula dislodgement from subcutaneous space, • Cannula malfunction (inability to pierce skin, bending, kinking, fluid leakage or other malfunction that might impact insulin infusion) • Mean visual analog scores (VAS) scores (0-100 mm) from Day of insertion through Day 7 of use • Mean difference of VAS scores (0-100mm) of CSII investigational sets and CSII control sets • Descriptive statistics of per subject term, severity, adverse device effects, and frequency of adverse events for each treatment • Descriptive statistics of per subject incidence of unanticipated adverse device effects
Study Population:	
Up to 30 adult participants, with the goal of having approximately 24 completers, may be enrolled, ages 18–70, diagnosed with Type 1 diabetes mellitus (T1DM) who have ≥ 6 months experience using rapid-acting insulin analog delivered via Medtronic MiniMed insulin pump and infusion sets. Only Medtronic pump models 530 and higher may be used.
 
Study participants will be drawn from existing T1DM patient populations meeting the study eligibility at each study center and from referral practices.

Phase:	Phase 1b
Description of Sites /Facilities Enrolling Participants:	This study will be conducted at no more than 5 centers in the United States. Each site will be qualified to conduct insulin treatment studies per a standardized euglycemic clamp protocol.

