
Description of Study Intervention:
	
Existing patient populations at each study center will be screened for study eligibility within 28 days of planned study enrollment. Participants without prior experience using the Dexcom G6 will be allowed up to 14 days of a run-in period to familiarize themselves with the CGM device. Eligible participants will complete written informed consent and be assigned a unique study ID.
 
Eligible participants will be randomized for Treatment Period A to either the Achilles investigational cannula or a Medtronic Silhouette control cannula using commercially available tubing, insulin lispro, insulin pumps and continuous glucose monitoring (CGM) equipment. After 2±1 week of washout each participant will enter Treatment Period B for a second 7-day period of catheter wear-time using the other infusion set.
 
On Day of Insertion (Day 0), participants will have the investigational Achilles infusion set or the control infusion set inserted by a qualified professional during a clinic visit. Participants will undergo training and be provided written instructions if infusion set change out is required during the 7-day wear period.
 
At the start of the study, participants will be provided with an insulin lispro vial (Humalog®, Eli Lilly and Co., Indianapolis, IN), a 23” tubing set compatible with the Achilles infusion set and Ascencia Contour Next glucose monitor plus test strips. Participants will also wear a study-provided Dexcom G6® (study continuous glucose monitor, to be used in real time mode) for the duration of the study. Participants will manage routine basal/bolus insulin therapy using these supplies and their current insulin pump for two home use wear periods of up to 7 days each. Finally, an Abbott Precision Xtra ketone monitor plus test strips will be provided for use in the event of hyperglycemia >250 mg/dL.
 
Visual inspection and photographic documentation of the Achilles and the comparator infusion set insertion site will be recorded at Day 0. Participants will be asked to conduct daily insertion site visual inspection and report/record site reactions, glycemic intervals and/or the need for infusion set change out (Days +1 to +7).
 
During a 7-day wear period, participants will undergo 4 in clinic euglycemic glucose clamps [Day of Insertion (DOI) and 3, 5, and 7 days later] to assess pharmacokinetics (PK) and pharmacodynamics (PD) of a bolus of lispro insulin (0.15 U/kg) when delivered using an insulin pump.
 
Upon completion of the first wear period (after 7 days or sooner, in the event that infusion set change out has occurred) and a 7-21 day washout period, participants will return to the investigational clinic site and will have a second infusion set inserted by a qualified professional. Sequence of control and investigational infusion set will be randomized.
 
It is expected that infusion set change out may be required prior to the end of the 7 day wear period. If necessary, participants will follow written instructions for change out to a commercial CSII set and return to the study center for visual and photographic evaluation of the insertion site. CGM data will be available to the study site in real time (and will be reviewed at each clinic visit) by using Dexcom Clarity software to access the individual participant’s Dexcom cloud account data. Data will be downloaded from the participant’s

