5.2 INCLUSION CRITERIA

In order to be eligible to participate in this study, an individual must meet all of the following criteria:

1. Participants are 18 – 70 years of age inclusive
2. Participant is in generally good health, as determined by the investigator
3. Participant is willing and able to individually complete written informed consent and agrees to comply with all study related testing and examinations
4. Participant must be geographically stable (e.g., expects to be available and capable of returning for all study specified test and examinations) during the study period
5. Participant has been diagnosed with T1DM for at least 12 months
6. C-peptide <0.6 nmol/L at screening
7. Participant has been using insulin pump therapy for at least 6 months and is currently using a Medtronic MiniMed pump, model series 530 or higher. Use of 670G in auto mode is acceptable.
8. Participant can provide a minimum of 14 days of insulin pump data to demonstrate pump use compliance

9. Participant is willing to perform frequent (4 times per day or more) self-monitoring of blood glucose (SMBG), including before meals and before bed, and using a meter and test strips provided by the sponsor during the two weeks of active treatment. This includes participants who are currently using real-time continuous glucose monitoring and may continue to do so, but must also collect SMBG values as instructed.
10. Participant is willing to perform serum ketone measurements whenever the blood glucose is determined to be greater than 250 mg/dL after extended fasting (e.g. overnight or more than five hours after a meal) using a ketone meter and strips provided by the sponsor
11. Participant has BMI in the range 20 – 35 kg/m² inclusive
12. Participant has experience infusing a rapid-acting insulin analog for at least 6 months
13. Participant has been using or is willing to use CGM (reading data available for at least 80% of time for a week of data collection during the screening period). Participants already using Dexcom G6 real time CGM may continue to use their own CGM unit; participants not using the G6 will be provided with a G6 monitor. All participants will be provided with CGM disposables for use during the treatment period.
14. Participant has ability to understand and comply with protocol procedures and to provide informed consent
15. HbA1c ≤8.5%
16. Stable body weight in the 3 months prior to enrollment (change in body weight <5%)

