6.4 STUDY COMPLIANCE

Study compliance will be assessed during the initial participant instruction period, and by review of daily diary and Dexcom G6 app entries. The investigational device will be applied to the study participant only after the participant has demonstrated an understanding of the study instructions, change out activities, the need to complete all study test requirements as written. If the study staff become aware of participant non-compliance to protocol requirements or follow-up evaluations, multiple attempts will be made to contact the participant to ensure patient safety and protocol adherence.

Adherence to glucose test procedure will be assessed by study personnel at site. All CRFs must be completed and CGM data will serve as electronic source documentation for hyperglycemic and hypoglycemic adverse events. Additionally, inquiries documented in clinic notes will be used for source documentation of patient-reported AEs. Photographs of infusion site will serve as source documentation for infusion site reactions.

The following will be collected regularly and documented:

- Study participant's insulin pump records
- Interstitial fluid glucose data from Dexcom G6® CGM throughout each study period (assessed by study staff at each study visit)
- BG measurements per Bayer Contour NEXT device will be used by participants for SMBG data collection as mandated by protocol requirements. Data will be downloaded at each clinic visit
- Serum ketones - measured by Abbott Precision Xtra Ketone meter (in case of hyperglycemia occurring during fasting or acute illness)
- Study participant diary (Pain score, SMBG)

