7 DISCONTINUATION AND WITHDRAWAL

7.1 DISCONTINUATION OF STUDY INTERVENTION

7.1.1 INFUSION SET CHANGE-OUT/EARLY DROPOUT

Independent of the time point for infusion set removal/change out, study staff is to follow the SOP for Infusion Set Removal and the reason for change-out is to be documented in the applicable source document and CRF.

We anticipate several commercial and/or investigational CSII catheters to fail prior to the fourth glucose clamp experiment on day 7. Participants will be instructed to contact the research investigator by telephone (24/7) to confirm the diagnosis of a failed CSII catheter. If the CSII catheter does not fail before day 7, the investigational/commercial CSII set will be removed upon completion of the clamp experiment on Visit 4A/Visit 4B. The site and cannula will be photographed, and the cannula inspected under a microscope.

The following are objective criteria that define a CSII catheter/infusion set failure:

1. The occurrence hyperglycemia (glucose >250 mg/dL) not responsive to a pump bolus dose where response to the bolus is defined as a fall of at least 50 mg/dL in blood glucose within one hour.
2. The occurrence of hyperglycemia (glucose >250 mg/dL) after prolonged fasting (e.g. overnight or more than 5 hours following a meal), not associated with acute intercurrent illness, but with a concurrent ketone level ≥ 0.6 mmol/L.
3. Signs of inflammation/infection at the infusion site including pain, erythema or induration >10 mm in diameter.
4. Occurrence of an insulin pump occlusion alarm signal.

In the case that any of the above occurs during home-use, the participant is asked to call the 24/7 helpline and confirm catheter failure with the study staff. The study participant will insert a new commercial CSII catheter (as used routinely by this patient) into the subcutaneous tissue at an alternate location and connect it to the insulin pump for routine glycemic management. The failed CSII catheter will be left in place. The participant is asked to measure erythema around the catheter and photograph the site. The study participant will return to the study site as soon as practicable so the research staff can remove and observe the failed CSII catheter. Study staff is to follow the SOP for catheter removal.

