4.3.3 Safety Variables

4.3.3.1 Device Malfunctions

4.3.3.1.1 Hyperglycemia (Glucose >250 mg/dL) not Responsive to Correction Bolus

This hyperglycemia episode is reported by the investigational site. Occurrence of these cases will be counted. A subject without any reported cases will have a count of 0.

4.3.3.1.2 Hyperglycemia with Elevated Ketones (Glucose >250 mg/dL and a Ketone Value ≥ 0.6 mMol/L) in the Absence of Evidence of Intercurrent Illness.

This hyperglycemia episode is reported by the investigational site. Occurrence of these cases will be counted. A subject without any reported cases will have a count of 0.

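### The home ketone-testing instruction waits for more than 2 hours above 250 mg/dL, while the ketone-based failure criterion and the other testing passages set no duration, so a few failures could be missed or recognised late

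*Protocol*

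**What the plan says.** Protocol 6.1.1.7 states what participants are to be told for the days at home. They should "monitor their blood ketone levels if their CGM or SMBG values are greater than 250 mg/dL for more than 2 hours", or test if signs or symptoms of ketoacidosis develop.

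Three other Protocol passages describe when ketones are measured:

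- Section 5.2, item 10, requires willingness to test "whenever the blood glucose is determined to be greater than 250 mg/dL after extended fasting".
- The synopsis (1.1, Description of Study Intervention) says a "ketone monitor plus test strips will be provided for use in the event of hyperglycemia >250 mg/dL".
- Section 6.4 lists ketone readings among the data collected, "in case of hyperglycemia occurring during fasting or acute illness".

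The event that these readings serve is criterion 2 for set failure in Protocol 7.1.1: glucose above 250 mg/dL after a prolonged fast, "not associated with acute intercurrent illness, but with a concurrent ketone level ≥ 0.6 mmol/L". The same event is a safety endpoint in the synopsis: "The occurrence of hyperglycemia (glucose >250 mg/dL) after prolonged fasting (e.g. overnight or more than 5 hours following a meal". When a criterion is met at home, "the participant is asked to call the 24/7 helpline and confirm catheter failure with the study staff".

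The SAP uses ketones twice. Section 4.3.2.7.1 includes hyperglycemia with a raised ketone reading in its definition of infusion set failure. Section 4.3.3.1.2 counts "Hyperglycemia with Elevated Ketones (Glucose >250 mg/dL and a Ketone Value ≥ 0.6 mMol/L) in the Absence of Evidence of Intercurrent Illness" and gives a participant with no reported case a count of zero.

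**The concern.** Criterion 2 is one of four events that define a failed set and lead to a change-out. Unlike the other three, it needs a measurement that only the participant can supply at home. A testing rule narrower than the event definition leaves some qualifying events without the reading that would identify them.

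Two things are at stake. The first is safety. Sets whose usual change interval is 72 hours (Protocol 2.1) are worn here for up to 7 days, and Protocol 2.3.3 relies partly on participant education to manage that risk. The second is ascertainment. In the SAP count, a participant who was never tested looks the same as one who tested negative, and set failures also feed a formal survival comparison.

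**Working it through.** No arithmetic applies and the plan gives no figure to reproduce. The check is a comparison of every passage that deals with ketone testing or the ketone-based event.

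| Place | What it governs | Glucose | Fasting condition | Duration condition |
|---|---|---|---|---|
| Protocol 6.1.1.7 | Instruction on when to test at home | >250 mg/dL | None | More than 2 hours (or ketoacidosis signs) |
| Protocol 5.2, item 10 | Willingness to test | >250 mg/dL | Yes | None |
| Protocol 1.1, intervention | Purpose of the ketone meter | >250 mg/dL | None | None |
| Protocol 6.4 | Data collected | No threshold given | Fasting or acute illness | None |
| Protocol 7.1.1, criterion 2 | Definition of failure | >250 mg/dL, ketones ≥0.6 mmol/L | Yes | None |
| Protocol 1.1, safety endpoints | Definition of endpoint | As criterion 2 | Yes | None |
| SAP 4.3.2.7.1 | Definition of failure | No threshold given; raised ketones | None | None |
| SAP 4.3.3.1.2 | Safety count | >250 mg/dL, ketones ≥0.6 mmol/L | None | None |

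**Step 1: which passages conflict.** The first four rows say when ketones are measured; the last four define an event. The direct conflict is therefore between 6.1.1.7 and the next three rows. An event definition does not need the same duration as a testing rule. The link to criterion 2 is ascertainment: without a concurrent reading it cannot be met.

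**Step 2: direction of the mismatch.** On duration, 6.1.1.7 is narrower than criterion 2. On fasting it is broader, because it also covers non-fasting episodes. The SAP events have no fasting condition, so tests done under 6.1.1.7 outside a fast can still contribute to the SAP counts.

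**Step 3: an illustrative case.** Suppose a participant wakes at 260 mg/dL after a short rise, gives a bolus, and falls by 50 mg/dL within the hour, to 260 − 50 = 210 mg/dL. Criterion 1 is not met, because the bolus worked. The 2 hours are never reached. Without ketoacidosis symptoms, 6.1.1.7 asks for no ketone test. If ketones were in fact ≥0.6 mmol/L with no intercurrent illness, criterion 2 was met and nobody knows it. If glucose instead stays above 250 mg/dL past 2 hours, the test is done, but later than item 10 of section 5.2 would have it.

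**Step 4: where a missed event goes.** In SAP 4.3.3.1.2 it becomes a zero in a tally that SAP 4.4.5.4 only describes. Through SAP 4.3.2.7.1 it is also absent from the life-table and log-rank comparison in SAP 4.4.4.2.1, unless the set later fails for another reason. That comparison uses days 0, 3, 5 and 7, so a short delay matters there only if it moves the failure across one of those days.

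**Step 5: size.** The documents give no rate or duration of fasting glucose above 250 mg/dL and no rate of ketone testing. The number of affected events cannot be estimated. A count of nights at home would measure opportunity, not events.

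**The case against.** The strongest reply is that the passages add up and do not contradict each other. Section 6.1.1.7 does not say that ketones are tested only in its two situations. Item 10 of section 5.2, the synopsis and section 6.4 together cover a fasting value above 250 mg/dL with no duration. Section 6.1.1.7 also refers to detailed participant instructions, including on managing catheter failure. Those are not among the documents and may already close the gap. The request in 7.1.1 to call when any criterion occurs presumes that participants know criterion 2.

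There are safeguards too. Protocol 2.3.3 lets staff follow interstitial glucose remotely and be texted on an alarm. Criteria 1, 3 and 4 need no ketone value. CGM time counts toward the 2 hours, so a participant who has been high overnight meets the trigger on waking. An episode that resolves within 2 hours after a bolus is weak evidence of a failed set.

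Most of this stands, and it makes the gap small. It does not remove it. Item 10 concerns willingness at enrolment, the synopsis passage concerns supply, and 6.4 concerns data collection. Section 6.1.1.7 is the one passage that says what participants will be told about when to test. Remote alarms show glucose, not ketones, and their threshold is not given.

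A reader might infer more: that failures are undercounted in favour of one device, or that the primary slope is biased because failure status can decide whether a later clamp takes place (Schedule of Activities, footnote 6). The documents support neither. The instruction is identical for both sets, no difference in short fasting episodes between them is shown, and the slope of log AUC does not use ketones.

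**Conclusion.** The inconsistency is real and the point is minor. The home instruction falls short of the plan's own failure definition for one kind of episode: at home, fasting, above 250 mg/dL for 2 hours or less, without ketoacidosis symptoms and not caught by another criterion. For longer fasting episodes the effect is a delayed test.

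The consequence is possible incomplete or late detection of criterion 2 failures. It reaches a descriptive safety count and the set-survival comparison. It is not a demonstrated bias, and its frequency is unknown.

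This rests on two assumptions: that participants follow 6.1.1.7 as written, and that the separate instructions add no fasting trigger. If either fails, the gap may not exist in practice, and what remains is wording to align.

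**What to change.** In Protocol 6.1.1.7, keep both existing triggers and add a third: test ketones at any glucose above 250 mg/dL after an overnight fast or more than 5 hours after a meal. Align the synopsis, item 10 of section 5.2 and section 6.4 with that combined rule, and carry it into the participant instructions. The burden is a few extra fingerstick tests; meters and strips are already supplied (Protocol 1.1 and 6.1.1.9).

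SAP 2.5 records that the study was terminated after the 7th participant completed, so the new wording can help only a successor protocol. For the data in hand, an optional listing could sit beside the SAP 4.3.3.1.2 count. It would show home episodes above 250 mg/dL with no ketone value in the downloaded meter data, so that untested episodes are visible as such. Fasting status would have to be inferred from pump boluses, because the diary contents in 6.1.1.7 do not list meal times. It should be marked as approximate, with a note that the SAP event has no fasting condition.

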6.1.1.8 STUDY TESTING COMPLETION

Discontinuation from the study intervention (infusion of insulin through a CSII catheter) does not mean discontinuation from the study, and remaining study procedures should be completed as indicated by the study protocol. The need to discontinue clinical use of the investigational or commercial CSII catheter prior to Visit 4A/Visit 4B is expected in some study participants and is not considered an adverse event. If an unplanned change-out of either the Achilles investigational cannula or control CSII set is required during a study visit/clamp, participant’s study participation in the respective treatment phase is considered completed at the time of infusion set change. If change-out occurs during *Treatment Phase 1*, the participant is asked to return for *Treatment Phase 2* after the washout period. If change-out occurs during Treatment Phase 2 the participant should return to the study site for a final study visit.

Before the study participant can be exited from the protocol, the following evaluations must be completed:

- Inspect/photograph insertion site
- Collect patient diary/photos

After completion of final evaluations, participant may be exited from the study.

